- Any clinically significant abnormal laboratory findings or other abnormal safety assessments which are associated with the underlying disease, unless judged by the investigator to be more severe than expected for the participant's condition.
- The disease/disorder being studied or expected progression, signs, or symptoms of the disease/disorder being studied, unless more severe than expected for the participant's condition.
- Medical or surgical procedure (eg, endoscopy, appendectomy): the condition that leads to the procedure is the AE.
- Situations in which an untoward medical occurrence did not occur (social and/or convenience admission to a hospital).
- Anticipated day-to-day fluctuations of preexisting disease(s) or condition(s) present or detected at the start of the study that do not worsen.
- Worsening of signs and symptoms of the malignancy under study should be recorded as AEs in the appropriate section of the CRF. Disease progression assessed by measurement of malignant lesions on radiographs or other methods should not be reported as AEs.

10.3.2. Definition of SAE

If an event is not an AE per definition above, then it cannot be an SAE even if serious conditions are met (eg, hospitalization for signs/symptoms of the disease under study).

An SAE is defined as any untoward medical occurrence that, at any dose:

a. Results in death

b. Is life-threatening

The term "life-threatening" in the definition of "serious" refers to an event in which the participant was at risk of death at the time of the event. It does not refer to an event that hypothetically might have caused death if it were more severe.

PFIZER CONFIDENTIAL

Page 102

c. Requires inpatient hospitalization or prolongation of existing hospitalization

In general, hospitalization signifies that the participant has been detained (usually involving at least an overnight stay) at the hospital or emergency ward for observation and/or treatment that would not have been appropriate in the physician's office or outpatient setting. Complications that occur during hospitalization are AEs. If a complication prolongs hospitalization or fulfills any other serious criteria, the event is serious. When in doubt as to whether "hospitalization" occurred or was necessary, the AE should be considered serious.

Hospitalization for elective treatment of a preexisting condition that did not worsen from baseline is not considered an AE.

d. Results in persistent disability/incapacity

- The term disability means a substantial disruption of a person's ability to conduct normal life functions.
- This definition is not intended to include experiences of relatively minor medical significance such as uncomplicated headache, nausea, vomiting, diarrhea, influenza, and accidental trauma (eg, sprained ankle) which may interfere with or prevent everyday life functions but do not constitute a substantial disruption.

e. Is a congenital anomaly/birth defect

f. Other situations:

- Medical or scientific judgment should be exercised in deciding whether SAE reporting is appropriate in other situations such as important medical events that may not be immediately life-threatening or result in death or hospitalization but may jeopardize the participant or may require medical or surgical intervention to prevent one of the other outcomes listed in the above definition. These events should usually be considered serious.
- Examples of such events include invasive or malignant cancers, intensive treatment in an emergency room or at home for allergic bronchospasm, blood dyscrasias or convulsions that do not result in hospitalization, or development of drug dependency or drug abuse.
- Progression of the malignancy under study (including signs and symptoms of progression) should not be reported as an SAE unless the outcome is fatal within the active collection period. Hospitalization due to signs and symptoms of disease progression should not be reported as an SAE. If the malignancy has a fatal outcome during the study or within the active collection period, then the event leading to death must be recorded as an AE on the CRF, and as an SAE with CTCAE Grade 5 (see the Assessment of Intensity section).

• Suspected transmission via a Pfizer product of an infectious agent, pathogenic or non-pathogenic, is considered serious. The event may be suspected from clinical symptoms or laboratory findings indicating an infection in a patient exposed to a Pfizer product. The terms "suspected transmission" and "transmission" are considered synonymous. These cases are considered unexpected and handled as serious expedited cases by pharmacovigilance personnel. Such cases are also considered for reporting as product defects, if appropriate.

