8.3.1. Time Period and Frequency for Collecting AE and SAE Information

The time period for actively eliciting and collecting AEs and SAEs ("active collection period") for each participant begins from the time the participant provides informed consent,

which is obtained before the participant's participation in the study (ie, before undergoing any study-related procedure and/or receiving study intervention), through and including a minimum of 90 calendar days, except as indicated below, after the last administration of the study intervention. NOTE, as indicated in Section 8.3.1.2: If a participant begins a new anticancer therapy, the recording period for nonserious AEs ends at the time the new treatment is started; however, SAEs must continue to be recorded on the CRF during the above-indicated active collection period.

Only SAEs will be actively elicited and collected after completion of the active collection period described above. The SAEs will be reported to Pfizer Safety on the CT SAE Report Form only if considered reasonably related to elranatamab.

Follow-up by the investigator continues throughout and after the active collection period and until the AE or SAE or its sequelae resolve or stabilize at a level acceptable to the investigator and Pfizer concurs with that assessment.

For participants who are screen failures, the active collection period ends when screen failure status is determined.

If the participant withdraws from the study and also withdraws consent for the collection of future information, the active collection period ends when consent is withdrawn.

If a participant definitively discontinues or temporarily discontinues study intervention because of an AE or SAE, the AE or SAE must be recorded on the CRF and the SAE reported using the Electronic Data Collection Tool.

Investigators are not obligated to actively seek AEs or SAEs after the participant has concluded study participation. However, if the investigator learns of any SAE, including a death, at any time after a participant has completed the study, and he/she considers the event to be reasonably related to the study intervention, the investigator must promptly report the SAE to Pfizer using the CT SAE Report Form.

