## 3.5.1. Adverse Events

An adverse event is considered treatment-emergent relative to study intervention if the adverse event start date is during the on-treatment period (including on the date of first dose).

AEs will be as characterized by type, severity, timing, seriousness, and relationship to study intervention.

AEs (except CRS and ICANS) will be graded by the investigator according to the NCI CTCAE version 5.0. CRS and ICANS will be graded by the investigator according to the ASTCT criteria. All AEs will be coded using the most current version of Medical Dictionary for Regulatory Activities (MedDRA).

TEAEs leading to dose interruption or dose reduction will be derived from the exposure CRF (dose adjustment reason as adverse event and actual dose taken of 0 for interruption and >0 for reduction) and then linked programmatically to the adverse event CRF by the AE identifier.

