#### 6.7.1. Adverse Events

All analyses will be based on treatment emergent adverse events (TEAEs) unless otherwise specified. Treatment emergent is defined in Section 3.5. AEs not considered treatment emergent will be flagged in data listings. Summaries of TEAEs due to COVID-19 may be produced if appropriate.

A high-level summary of adverse events (all causality and treatment-related, separately) will include the number and percent of participants with:

- Any TEAEs;
- Serious TEAEs;
- Grade 3-4 TEAEs;
- Grade 5 TEAEs;
- TEAEs leading to dose interruptions;
- TEAEs leading to dose reductions;
- TEAEs leading to dose interruptions or reductions;
- TEAEs leading to permanent discontinuation of study intervention;
- CRS;

- ICANS;
- Peripheral neuropathy.

Seriousness, toxicity grade, and withdrawal from drug are as reported by the investigator on the adverse event CRF.

An event will be considered treatment-related if the investigator considered the event as related to the study drug or if relationship is missing.

For all the AE summaries by SOC and PT, or PT only, the following cytopenias will be clustered. Each participant will be counted only once within each SOC and clustered terms. However, the number of total events will be based on the individual PTs.

- Thrombocytopenia (PT=Thrombocytopenia; Platelet count decreased);
- Anaemia (PT=Anaemia; Haemoglobin decreased, Red blood cell count decreased, Haematocrit decreased, Normochromic anaemia, Normocytic anaemia, Normochromic normocytic anaemia);
- Neutropenia (PT=Neutropenia; Neutrophil count decreased, Neutrophil percentage decreased, Cyclic neutropenia, Agranulocytosis, Granulocytopenia, Granulocyte count decreased);
- Leukopenia (PT=Leukopenia; White blood cell count decreased);
- Lymphopenia (PT=Lymphopenia; Lymphocyte count decreased, Lymphocyte percentage decreased, CD4 lymphocytes decreased, CD4 lymphocyte percentage decreased, CD8 lymphocytes decreased, CD8 lymphocyte percentage decreased).

Summaries by SOC and PT by alphabetical order for SOC and by descending order of frequency for PT in two cohorts combined will be provided for:

- TEAEs (all causality and treatment-related);
- TEAEs by maximum severity grade (all causality and treatment-related);
- TEAEs with Grade 3-4 (all causality and treatment-related);
- TEAEs leading to death (all causality and treatment-related);
- TEAEs leading to dose interruptions (all causality);
- TEAEs leading to dose reductions (all causality);

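### Protocol 10.3.2 sets two incompatible windows for recording fatal myeloma, so a late myeloma death whose fatal event is dated on treatment can enter or miss the fatal-TEAE tables depending on the site

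*Protocol*

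**What the plan says.** **Protocol 10.3.2 (Definition of SAE), one bullet.** The first sentence says that progression of the malignancy "should not be reported as an SAE unless the outcome is fatal within the active collection period". The last sentence sets a different condition, "If the malignancy has a fatal outcome during the study or within the active collection period", and attaches an obligation to it: "then the event leading to death must be recorded as an AE on the CRF, and as an SAE with CTCAE Grade 5".

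**Length of the two windows.** Protocol 8.3.1 runs active collection from consent through "a minimum of 90 calendar days, except as indicated below, after the last administration of the study intervention". Protocol 4.4 keeps the study open until every participant has been followed for survival for at least 2 years from enrollment.

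**Neighbouring rules.** Protocol 8.3.1.2 ties CRF recording of AEs and SAEs to the active collection period. For the time after that period, 8.3.1 says that SAEs continue to be collected, and adds: "The SAEs will be reported to Pfizer Safety on the CT SAE Report Form only if considered reasonably related to elranatamab". The summary table in 10.3.3 has all SAEs recorded and all reported.

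**SAP.** Section 3.5 ends the on-treatment period at 90 days after last dose, or on the day before new anticancer therapy if that is earlier. Later safety data are listed only. Section 3.5.1 states: "An adverse event is considered treatment-emergent relative to study intervention if the adverse event start date is during the on-treatment period". Section 6.7.1 plans a count of Grade 5 TEAEs and a table line beginning "TEAEs leading to death (all causality and treatment-related". Neither is limited by date of death, and neither separates out study-disease terms. Section 6.7.2 tabulates deaths from the death and survival follow-up CRFs.

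**The concern.** A site that follows the first sentence will not report a myeloma death in long-term follow-up as an SAE. A site that follows the last sentence must record it as a Grade 5 AE and SAE. Both sites are complying with the protocol.

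The trial is single-arm, so there is no concurrent control rate of fatal adverse events in which the same ambiguity would appear. The all-causality fatal-TEAE rate is read at face value, and it should not depend on which sentence a site applied. The safety database and the listings are exposed to the same variation.

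**Working it through.** The plan gives no figure to reproduce on this point. The check compares the two recording windows with the SAP's onset-based window, and then sizes one reclassified death.

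**Inputs**
- Active collection: to at least 90 days after last dose (Protocol 8.3.1).
- Study duration: at least 2 years of survival follow-up from enrollment (Protocol 4.4).
- On-treatment period: to last dose + 90 days, or the day before new anticancer therapy if earlier (SAP 3.5).
- TEAE status: set by AE start date (SAP 3.5.1).
- Treated participants: 123 in Cohort A, 64 in Cohort B (Protocol 9.2), so 123 + 64 = 187 combined.

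**Myeloma deaths by date of death and onset of the fatal event**

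| Case | Death | Onset of fatal event | First sentence | Last sentence | Fatal-TEAE count |
|---|---|---|---|---|---|
| a | Within active collection | Any | Grade 5 SAE | Grade 5 SAE | Same under both |
| b | After active collection | After the on-treatment period | Not an SAE | Grade 5 SAE | Same under both: not a TEAE; only listings and the safety database differ |
| c | After active collection | Within the on-treatment period | Not a fatal SAE | Grade 5 SAE | **Differs** |

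Only case c reaches the fatal-TEAE tables.

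**Illustration (hypothetical dates).** Last dose is Day 143, worsening begins on Day 150, and the participant dies of myeloma on Day 400. Death falls 400 − 143 = 257 days after last dose, well beyond 90. Without new therapy, the on-treatment period ends on Day 143 + 90 = 233.
- Under the last sentence, with the fatal event dated to Day 150, it is a Grade 5 TEAE, because 150 is not later than 233.
- Under the last sentence, with the fatal event dated to Day 400, it is not a TEAE, because 400 is later than 233.
- Under the first sentence, there is no fatal SAE at all. The Day 150 symptoms may still be on the CRF as a non-fatal AE.

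Neither document says which of the two onset dates to record. Membership of case c is therefore itself open to site practice.

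**Size per case-c death**
- Cohort A: 1/123 = 0.8 percentage points.
- Cohort B: 1/64 = 1.6 percentage points.
- Combined: 1/187 = 0.5 percentage points.

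For k such deaths the shift is k/123, k/64 or k/187. The documents do not give k.

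**The case against.** The strongest reply is that the main text already points to the narrow window and that the SAP filters out most late deaths. Protocol 8.3.1.2 does favour active collection only, and case b shows that the onset rule keeps many late deaths out of the tables. Protocol 10.3.1 also says that progression established by measurement should not be reported as an AE, so the date of a progression assessment is not automatically the onset of a fatal event. All of this stands, and it limits the consequence. It does not remove the conflict. The last sentence of the bullet is mandatory and wider than 8.3.1.2, and 10.3.1 also asks for worsening signs and symptoms of the malignancy to be recorded as AEs. These can begin on treatment.

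A reader might infer more than the documents support in four ways:
- **A third conflicting rule.** Section 10.3.2 also says "If an event is not an AE per definition above, then it cannot be an SAE even if serious conditions are met". This is a general rule. The bullet on fatal malignancy is a specific exception to it, so the two do not conflict.
- **Unrelated SAEs no longer collected after 90 days.** Section 8.3.1 restricts reporting to the sponsor's safety group to related events. It does not restrict collection in that way.
- **A clash with the SAP 6.7.2 death table.** That table counts deaths by date of death from separate CRFs, while 6.7.1 counts adverse events by onset. They are different quantities and need not agree.
- **A large shift in the fatal-TEAE rate.** Any total needs the proportion dying, the share due to myeloma, the share dying after active collection, and the share with on-treatment onset. None is in the documents. The final analysis can also be triggered after two post-baseline assessments, and data after the cutoff are excluded (SAP 5.1.2, 5.2.1), so few late deaths need have occurred by then.

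**Conclusion.** The contradiction within 10.3.2 is real, and no other section clearly settles it. It allows a myeloma death after the active collection period to be a Grade 5 SAE at one site and unrecorded as such at another. It changes the Grade 5 TEAE count and the TEAEs-leading-to-death table only when the fatal event is dated within the on-treatment period. The shift is then 0.8 points per death in Cohort A and 1.6 in Cohort B, with the number of deaths unknown.

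This rests on two assumptions: that some sites follow each sentence, and that some fatal events are dated to the start of deterioration rather than to death. It would be wrong to conclude that every late myeloma death moves the fatal-TEAE rate. ORR, OS and the SAP 6.7.2 death table do not draw on these AE records. The Grade 5 enrollment-hold rules cover CRS, ICANS and treatment-related events, so an unrelated myeloma death does not enter them. The point concerns consistency of safety reporting and is worth correcting. It does not bear on the efficacy conclusions.

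**What to change.** **Protocol 10.3.2.** Reconcile the two sentences so that one window applies, consistent with 8.3.1 and 8.3.1.2. For example, strike from the last sentence the words that extend it to the whole study, leaving the active collection period. State which onset date is recorded for the fatal event: start of the deterioration or date of death.

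**SAP 6.7.1.** Present Grade 5 TEAEs and TEAEs leading to death with and without study-disease preferred terms. Flag study-disease deaths more than 90 days after last dose.

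**What not to do.** Do not limit all fatal TEAEs to deaths within 90 days of last dose. An infection that starts on treatment and proves fatal on day 100 after the last dose would then leave the tables, although 8.3.1 requires events to be followed beyond the active collection period.

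**Cost.** The protocol change is a short clarification, but it needs IRB/EC approval (Protocol 10.1.1). Enrollment closed in January 2022, so it cannot undo records already made. The SAP change adds one or two table rows, uses dates and terms already collected, and shows the effect of past differences in site practice.

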10.3.3. Recording/Reporting and Follow-up of AEs and/or SAEs

AE and SAE Recording/Reporting

The table below summarizes the requirements for recording adverse events on the CRF and for reporting serious adverse events via the Electronic Data Collection Tool or on the CT SAE Report Form to Pfizer Safety (see sections 8.3.1, 8.3.5 and 8.3.10 for guidance). These requirements are delineated for 3 types of events: (1) SAEs; (2) nonserious adverse events (AEs); and (3) exposure to the study intervention under study during pregnancy or breastfeeding, and occupational exposure.

It should be noted that the Electronic Data Collection Tool and the CT SAE Report Form for reporting of SAE information are not the same as the AE page of the CRF. When the same data are collected, the forms must be completed in a consistent manner. AEs should be recorded using concise medical terminology and the same AE term should be used on both the CRF and the CT SAE Report Form for reporting of SAE information.

Safety Event	Recorded on the CRF	Reported via the Electronic Data Collection Tool or on the CT SAE Report Form to Pfizer Safety Within 24 Hours of Awareness		
SAE	All	All		
Nonserious AE	All	None		
Exposure to the study intervention under study	All AEs/SAEs associated with exposure during	All (and EDP supplemental form for EDP)		
during pregnancy or breastfeeding, and occupational exposure	pregnancy or breastfeeding Occupational exposure is not recorded.	Note: Include all SAEs associated with exposure during pregnancy or breastfeeding. Include all AEs/SAEs associated with occupational exposure.		

- When an AE/SAE occurs, it is the responsibility of the investigator to review all documentation (eg, hospital progress notes, laboratory reports, and diagnostic reports) related to the event.
- The investigator will then record all relevant AE/SAE information in the CRF.
- It is **not** acceptable for the investigator to send photocopies of the participant's medical records to Pfizer Safety in lieu of completion of the Electronic Data Collection Tool / CT SAE Report Form/AE/SAE CRF page.
- There may be instances when copies of medical records for certain cases are requested by Pfizer Safety. In this case, all participant identifiers, with the exception of the participant number, will be redacted on the copies of the medical records before submission to Pfizer Safety.
- The investigator will attempt to establish a diagnosis of the event based on signs, symptoms, and/or other clinical information. Whenever possible, the diagnosis (not the individual signs/symptoms) will be documented as the AE/SAE.

Assessment of Intensity

The investigator will report severity for each AE and SAE reported during the study based on the National Cancer Institute Common Terminology Criteria for Adverse Events (CTCAE) Version 5.0.

GRADE	Clinical Description of Severity
1	MILD adverse event
2	MODERATE adverse event
3	SEVERE adverse event
4	LIFE-THREATENING consequences; urgent intervention indicated
5	DEATH RELATED TO adverse event

The severity of CRS and ICANS will be graded according to ASTCT criteria (Lee et al,2019b). See Appendix 11.

Assessment of Causality

• The investigator is obligated to assess the relationship between study intervention and each occurrence of each AE/SAE.

- A "reasonable possibility" of a relationship conveys that there are facts, evidence, and/or arguments to suggest a causal relationship, rather than a relationship cannot be ruled out.
- The investigator will use clinical judgment to determine the relationship.
- Alternative causes, such as underlying disease(s), concomitant therapy, and other risk factors, as well as the temporal relationship of the event to study intervention administration, will be considered and investigated.
- The investigator will also consult the IB and/or product information, for marketed products, in his/her assessment.
- For each AE/SAE, the investigator must document in the medical notes that he/she has reviewed the AE/SAE and has provided an assessment of causality.
- There may be situations in which an SAE has occurred and the investigator has minimal information to include in the initial report to the sponsor. However, it is very important that the investigator always make an assessment of causality for every event before the initial transmission of the SAE data to the sponsor.
- The investigator may change his/her opinion of causality in light of follow-up information and send an SAE follow-up report with the updated causality assessment.
- The causality assessment is one of the criteria used when determining regulatory reporting requirements.
- If the investigator does not know whether or not the study intervention caused the event, then the event will be handled as "related to study intervention" for reporting purposes, as defined by the sponsor. In addition, if the investigator determines that an SAE is associated with study procedures, the investigator must record this causal relationship in the source documents and CRF, and report such an assessment in the dedicated section of the Electronic Data Collection Tool or CT SAE Report Form and in accordance with the SAE reporting requirements.

Follow-up of AEs and SAEs

• The investigator is obligated to perform or arrange for the conduct of supplemental measurements and/or evaluations as medically indicated or as requested by the sponsor to elucidate the nature and/or causality of the AE or SAE as fully as possible. This may include additional laboratory tests or investigations, histopathological examinations, or consultation with other healthcare providers.

- If a participant dies during participation in the study or during a recognized followup period, the investigator will provide Pfizer Safety with a copy of any postmortem findings including histopathology.
- New or updated information will be recorded in the originally completed CRF.
- The investigator will submit any updated SAE data to the sponsor within 24 hours of receipt of the information.

